**Brief objectives:**

The aim of this study is to evaluate the association of laminar airflow versus turbulent airflow ventilation on prosthetic joint infection and on any revision.

## Abstract

**Background:** During surgery, bacteria in the air in the operating room (OR) is considered a cause of periprosthetic joint infection (PJI). Previously, turbulent airflow (TAF) has been used in ORs. Later, laminar airflow (LAF) has been developed, which minimize the number of colony forming units in the air. However, most studies show no benefit of LAF regarding PJI incidence.

**Aim:** To evaluate the association of LAF versus TAF ventilation on primary PJIs in 90 and 365 days in total hip arthroplasties (THAs) using the Danish hip arthroplasty register (DHR) and the Danish microbiology register (MiBa)

**Methods:** All THAs performed in Denmark in 2010-2020 are identified in DHR. Through DHR, revisions and type of ventilation system is identified. PJI is defined using a validated method combining MiBa with DHR, where infection is defined as two or more positive identical bacteria cultures or is registered by the surgeon as PJI. The risk of PJI s in THAs performed in TAF are compared with THAs performed in LAF using Cox regression models adjusting for confounders.

**Use and relevance:** PJIs are extremely costly and cause a significant morbidity and mortality for the patient. When constructing or renovating a hospital, it is crucial to choose a ventilation system that minimizes PJIs, while being cost-efficient. Previous studies on LAF vs TAF are based on data from national registers. Since registration of PJI is reported immediately to DHR and other arthroplasty registers after surgery, the microbiology results are not taken into consideration when the revision cause is reported. This study is novel, because it gives a more accurate picture of the PJI incidence and can be part in guiding the decisions when renovating or designing new hospitals, in order to decrease the risk of PJI.

## Rationale and background

Prosthetic joint infection (PJI) is one of the most feared complication after total hip arthroplasty (THA), with increased mortality and morbidity, as well as a significant cost for society (1–4). Since the 1960s, in addition to systemic prophylactic antibiotics and antibiotic-laden bone cement, efforts have been made to make the air in the operating rooms (OR) as clean as possible with filtering and replacement of the air (5).

This has led to the current official PJI incidence of 0.57-0.80 % in the first year after surgery according to the Danish Hip Arthroplasty Register (DHR) and the Swedish Hip Arthroplasty

Register (SHAR), even though the true incidence of PJI probably is about 40 % higher, due to under-registration in the registers following revision surgery (6,7).

The risk of PJI is potentially affected by contamination in the OR (5,8–10), patient related risk factors (11,12) and prosthesis factors. The prosthesis factors include type of implant and implant fixation method. Cemented implants have a lower overall revision rate, although the results are not unanimous when it comes to revision due to PJI (13–16).

The risk of contamination in the OR is affected by the cleanliness of the air (5,17–21). There are two different types of ventilation systems used to achieve a clean environment in an OR. The first is turbulent airflow (TAF), where the air is continuously replaced with filtered ultra-clean air that trickles down from the ventilation shaft. The second is laminar airflow (LAF) where the ultra-clean air flows in a single direction, with the goal to prevent particles carrying bacteria, that are floating in the air, to land on the patient or sterile equipment (17,22).

LAF decreases the bacterial load significantly in the OR, measured in CFUs (17–21). However, the number of CFUs has not been found to correlate with the incidence of PJI in real world data, where most studies show no advantage of LAF compared to TAF. Only one major observational study shows that LAF decreases the risk of infection in a subgroup of LAF (23). All other register studies show no difference between LAF and TAF or a higher risk for PJI with LAF (24–28). There are no randomized, controlled trials (RCTs) comparing modern-day ventilation systems when it comes to the PJI incidence in THAs.

There are no randomized, controlled trials (RCTs) comparing modern-day ventilation systems when it comes to the PJI incidence in THAs. However, in 1982, an RCT was conducted by Lidwell et al., comparing different ultraclean air flow systems, including LAF, with standard operating room ventilation at the time. In this study, there was a significant difference in PJI incidence with 2.2 % PJIs in the standard OR group and 1.0 % in the ultraclean group. However, these standard ORs had much higher bacterial contamination, with a median of 164 CFUs/m^3 (29), compared to modern-day TAF ORs, that have a median ranging from 4,5-22 CFU/m^3 (18,19,22). The ultraclean group had a median of 2-10 CFUs/m^3, thus it resembles modern-day TAF ORs, both in bacterial load and PJI rate (29).

Due to additional costs in building and maintaining LAF systems, a public analysis was conducted in Denmark in 2011 to compare the cost-effectiveness of LAF and TAF. When considering the estimated annual costs, which included operational expenses, depreciation, and interests, LAF ORs were estimated to cost 508,732 DKK per year, whereas TAF ORs were projected to cost 304,530 DKK per year. As a result, there was an annual cost difference of 204,202 DKK (€27,000) per unit, with LAF being 67 % more expensive than TAF. A PJI was estimated to cost the society around 204,000 DKK in the same year (4).

An issue in the previous studies on PJI in LAF and TAF are that they are epidemiological and rely solely on the PJI diagnosis reported to the different registers. However, diagnosing a PJI is not always evident in a clinical setting. It has been shown that the DHR is lacking both registration of revisions and later confirmed PJI (30), and a lack of registered PJI revisions has also been observed in the Swedish hip arthroplasty register (SHAR) (7).

The PJI diagnosis in the DHR can be greatly improved, if combined with the Danish Microbiology Database (MiBa) (31). When validating the diagnosis PJI in DHR, the sensitivity was found to be only 67 %. When using an algorithm including data from MiBa, sensitivity increased to 90 %, without providing more false positives. A simplified algorithm utilizing MiBa data exhibited no statistically significant difference when compared to the more extensive algorithm employed in the validation study by Gundtoft et al. (30,31). This simplified algorithm, which doesn't require access to medical records, will be applied in the criteria for the primary outcome.

Additionally, previous studies show that one positive bacterial sample at a clinically aseptic revision increases the risk of an occult infection, diagnosed later at a re-revision (32). This will be investigated as well.

Thus, using these new and well validated methods, the investigators aim to estimate the risk of PJI with LAF versus TAF ventilation better than has been done in previous studies.

## Data sources

**The Danish Civil Registration System (Centrale Person Register, CPR)** contains information including vital status and time of emigration on all Danish residents (33). All Danish residents and citizens are assigned a unique and permanent individual identification number (CPR number) at birth or upon immigration. It enables an unambiguous linkage between different registers and allows an individual follow-up over time (34).

**The Danish National Patient Register (NPR)** collects data of all Danish residents contact to a public hospital, including date, performed examinations or surgical procedures and diagnosis, classified by International Classification of Diseases (ICD) (35). The data includes both outpatient and inpatient contacts and is linked with the patient's CPR number (36).

**The Danish Hip Arthroplasty Register (DHR)** collects data including type of OR ventilation from all THAs performed in Denmark, including primary THAs as well as revisions (37). It is mandatory for all surgeons performing THAs to report to the register, which results in high completeness. The data is previously validated (38). In the case of a revision, the surgeon reports the indication immediately after surgery (39). The revisions performed within 90 and 365 days are located in the DHR, which also contains information from the NPR about revisions.

**The Danish Microbiology Database (MiBa)** automatically collects all microbiology results from all departments of clinical microbiology in Denmark since 2010, which are then stored electronically using the patient's CPR number as patient identifier (40). The register completeness is previously validated (41). The data will more specifically be extracted from the Healthcare-Associated Infections Database – HAIBA, a part of MiBa.

**The Danish National Prescription Register (DNPR)** collects detailed information on redeemed prescriptions in Denmark since 1995. It is previously validated and has a high degree of completeness and is frequently used in epidemiological research (42).

**Income Statistics Register** – The register contains income data on more than 160 variables including salaries and savings of people with a Danish income and is widely used in research. Each individual is identified with an unambiguous CPR number (43).

**Danish Education Register** – The register has a high coverage on education level, both among people born in Denmark and immigrants and is widely used in research. Each individual is identified with an unambiguous CPR number (44).

## Variables

The investigators will look at several variables and adjust for these where needed. The variables obtained from DHR is body mass index (BMI), age, gender, time of surgery, diagnosis, type of prosthesis and fixation method, whether cement is used and if it contains antibiotics, previous operations on the same hip and ASA score. ASA score and BMI are only available from 2017 and onwards in DHR.

From NPR, concomitant diagnoses will be obtained to produce an Elixhauser comorbidity score, and socioeconomic factors, such as income and education will be obtained from the Danish Income Statistics Register and Education Register.

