The definition of PJI is based on the studies by Gundtoft et al. (30,31), where it has been concluded, that the validity of the PJI diagnosis is greatly improved when using these criteria, which are validated specifically for DHR. The original study by Gundtoft et al. used an extensive algorithm to determine if a PJI was present. However, there was no statistically significant difference between the extensive algorithm and a simplified algorithm, that defines a PJI as two or more positive identical bacterial samples (30).

The investigators definition is in line with international consensus (48) and does not differ greatly from the definition made by the European Bone and Joint Infection Society (EBJIS) (49), although erythrocyte sedimentation rate, aspiration of joint fluid, white blood cell count in joint fluid and histological examination of intraoperative tissue biopsies are not routinely used in Denmark. Thus, these criteria are not used. Sinus tract communication with the hip joint or an opening to the hip joint is expected to cause the surgeon to register the diagnosis “infection” in DHR upon revision. Data for this analysis will be extracted from DHR and

HAIBA. For the revision surgery to be registered in HAIBA, at least three biopsies at the revision surgery are required, hence this is a part of the criteria (50).

*Secondary endpoints:*

- 1) Revision registered as aseptic loosening in DHR.
- 2) Any revision registered in DHR.

Aseptic loosening is a separate endpoint, since it has been shown that aseptic loosening might in fact turn out to be a PJI and is thus a point of interest (32,51,52).

*Sensitivity analyses:*

In addition, the following sensitivity analyses will be made:

- a) Alternative outcome: Primary revision registered as PJI or with at least one positive biopsy of a bacterium.
- b) Alternative outcome: Primary revision reported to DHR with at least one positive biopsy of a bacterium AND the prescription of a relevant antibiotic, specified in appendix A.
- c) Analysis for the primary endpoint, but for data collected between 2017-2020, allowing for adjustment for BMI and ASA as possible confounders, as these variables are only registered in this period

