#### Statistical analysis:

Descriptive results for continuous variables will be shown as mean(SD)/median(range) depending on the distribution of the variables. Categorical variables will be presented using frequencies and percentages. Persons operated in LAF and TAF ORs are compared using t-tests/Wilcoxon-tests and chi-square tests, respectively. This is supplemented with cumulative incidence plots showing risk of infection (primary outcome) for LAF and TAF, regarding revision due to other causes and death as competing events. The two groups are compared using Grays test. To fulfill the requirements at Statistics Denmark about data on individual persons, a smooth curve is used to make the plot rather than the statistical correct step-function. Information at time 90 and 365 days after the operation will be presented. This type of plot will be used for all endpoints.

For the primary endpoint, two Cox regression analyses will be performed with the time to PJI as outcome. One model will only cover the first 90 days of follow-up, the other will cover all 365 days of follow-up. Censoring is made at time of revision due to other causes than PJI, death, emigration, and end of follow-up (365 days after operation), whichever comes first. Bilateral THA will be included in the model as two observations with inclusion of a time-dependent variable conditioning on the status of the other hip (53). A robust sandwich covariance matrix estimate is used to account for the intrapersonal dependence.

The model will include the following potential confounders:

Education, age, comorbidities, gender, previous hip surgery, primary diagnosis, type of cement, type of fixation, year of surgery, income and duration of surgery. ASA and BMI will be adjusted for in sensitivity analysis c). A direct acyclic graph is used when determining the variables needed to adjust for.

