## Appendix A

List of antibiotics screened for 2 weeks after revision, originating from the study by Lidgren et al. from 2014 (56), adapted to Danish conditions

J01CA04 Amoxicillin  
J01CR02 Amoxicillin and clavulanic acid  
J01CE02 Phenoxymethylpenicillin  
J01CF05 Flucloxacillin  
J01CF01 Dicloxacillin  
J01FA01 Erythromycin  
J01FA06 Roxithromycin  
J01FA09 Clarithromycin  
J01FA10 Azithromycin  
J01XC01 Fucidin  
J04AB02 Rifampicin  
J01FF01 Clindamycin  
J01XX08 Linezolid  
J01XD01 Metronidazole  
J01MA02 Ciprofloxacin  
J01MA12 Levofloxacin  
J01MA14 Moxifloxacin  
J01EE01 Sulfametoxazol and trimetoprim

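### Comorbidity is measured from hospital diagnoses alone and may be under-captured; pre-operative prescriptions from a register already in the plan would improve it cheaply in all study years

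*Combined protocol and SAP*

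**What the plan says.** - **Source of comorbidity (Variables).** "From NPR, concomitant diagnoses will be obtained to produce an Elixhauser comorbidity score". No other source is named.
- **Coverage of NPR (Data sources).** The register "collects data of all Danish residents contact to a public hospital". The section adds: "The data includes both outpatient and inpatient contacts". Primary care is not mentioned.
- **Population (Methods, Study population).** All adult primary hip replacements in the arthroplasty register (DHR) from 2010 to 2020, except tumour cases and erroneous registrations. It is not limited to public hospitals.
- **Prescription register (Data sources).** DNPR "collects detailed information on redeemed prescriptions in Denmark since 1995" and is said to be highly complete.
- **Use of DNPR.** Only sensitivity analysis b), whose outcome requires a positive biopsy "AND the prescription of a relevant antibiotic, specified in appendix A". Appendix A is headed "List of antibiotics screened for 2 weeks after revision" and contains antibiotics only.
- **Primary model (Statistical analysis).** The confounders are "Education, age, comorbidities, gender, previous hip surgery, primary diagnosis, type of cement, type of fixation, year of surgery, income and duration of surgery". For the two remaining health measures, "ASA and BMI will be adjusted for in sensitivity analysis c"; that analysis is restricted to 2017-2020 because DHR lacks both variables before then.

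**The concern.** The Rationale accepts that patient-related factors affect infection risk. In the primary models those factors are represented mainly by age, gender, primary diagnosis, socioeconomic position and the comorbidity score. A patient whose diabetes, lung disease or steroid treatment is handled outside public hospitals may enter the model with a lower score than their health warrants.

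If such patients are spread unevenly over LAF and TAF rooms, adjustment for the score removes only part of the confounding and the rest goes into the LAF/TAF hazard ratio. A national cohort gives a small standard error, so even a modest systematic shift matters for a result intended to inform hospital design. The plan already links a register that could reduce the problem in every inclusion year, but nothing redeemed before surgery enters any model.

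**Working it through.** The plan gives no event count, power or bias figure on this point, so there is nothing to reproduce. The check has two parts.

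**1. Reading the sections together.** Comorbidity comes from NPR only; NPR is described as public-hospital contacts; the cohort is every eligible hip replacement in DHR. Eligibility is therefore wider than the described coverage of the comorbidity source. DNPR starts in 1995, 15 years before the first inclusion year, so a 12-month window before surgery is available for every patient resident in Denmark throughout that window. BMI and ASA cover 4 of the 11 inclusion years (2017-2020).

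**2. Illustrating the size.** Every input in this step is an assumption, because the documents give no LAF/TAF case mix and no figure for NPR completeness. Take one binary condition with prevalence p1 = 0.15 in one group and p0 = 0.10 in the other, hazard ratio r = 2 for infection, no true ventilation effect, and a record with sensitivity s and no false positives.

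- With nothing recorded, the spurious hazard ratio is [1 + p1(r − 1)] / [1 + p0(r − 1)] = 1.15 / 1.10 = 1.045.
- With partial recording, bias remains only among patients without a record. Prevalence there is q = p(1 − s) / (1 − ps), and the ratio in that stratum is b = [1 + q1(r − 1)] / [1 + q0(r − 1)]. In the recorded stratum the ratio is 1. The two are combined with Mantel-Haenszel-type weights for equal groups.
- At s = 0.5: q1 = 0.075 / 0.925 = 0.0811 and q0 = 0.050 / 0.950 = 0.0526, so b = 1.0811 / 1.0526 = 1.0270. The weights are (0.925 × 0.950 / 1.875) × 1.0526 = 0.4933 unrecorded and (0.075 × 0.050 / 0.125) × 2 = 0.0600 recorded. The combined ratio is (0.4933 × 1.0270 + 0.0600) / 0.5533 = 1.024.
- At s = 0.7: q1 = 0.045 / 0.895 = 0.0503, q0 = 0.030 / 0.930 = 0.0323, b = 1.0175, weights 0.4708 and 0.0840. The combined ratio is (0.4708 × 1.0175 + 0.0840) / 0.5548 = 1.015.

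| Share recorded | 0% | 30% | 50% | 70% | 90% |
|---|---|---|---|---|---|
| 15% vs 10%, HR 2 | 1.045 | 1.033 | 1.024 | 1.015 | 1.005 |
| 20% vs 10%, HR 2 | 1.091 | 1.066 | 1.049 | 1.030 | 1.010 |
| 12% vs 10%, HR 1.5 | 1.010 | 1.007 | 1.005 | 1.003 | 1.001 |

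With p1 = p0 every entry is 1.

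**Comparison with sampling error.** Assume 80,756 to 100,000 hips; the lower figure is the size of an earlier DHR study in the reference list. Assume equal groups and a one-year risk of 0.80-1.12%, which is the Rationale's 0.57-0.80% raised by its 40% under-registration (0.57 × 1.4 = 0.80; 0.80 × 1.4 = 1.12). Events are 80,756 × 0.0080 = 646 to 100,000 × 0.0112 = 1,120. The standard error of the log hazard ratio is 2/√events = 0.079 to 0.060.

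At 50% recorded, ln(1.024) = 0.024 is 0.30-0.40 standard errors. At 70%, ln(1.015) = 0.015 is 0.19-0.25. The two-sided error rate, P(Z > 1.96 − shift) + P(Z < −1.96 − shift), is then 6.1-6.8% at 50% recorded and 5.4-5.7% at 70%, against a nominal 5%.

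**The case against.** **The conditions are not wholly unadjusted.** A reader might infer that anything treated outside hospital is missing from the model. The documents do not support that. NPR holds both inpatient and outpatient contacts, and a condition managed in general practice can still be coded at any of them, including the hip admission. The defect is under-capture, of unknown extent.

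**The larger error rates need extreme inputs.** The same scenario with zero capture and 1,120 events gives a shift of 0.74 standard errors and an error rate of about 11.5%. The arithmetic is right, but it also assumes equal groups; an 80/20 split alone lowers the figure to about 9%. It is not a fair estimate of the problem.

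**The imbalance is assumed.** No document shows that case mix differs between LAF and TAF rooms. What matters is the imbalance left after all listed covariates, which the illustration ignores. Several conditions need not add up either, since they overlap within patients and imbalances can run in opposite directions. This stands, and it is why no size can be claimed as established.

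**Sensitivity analysis c) is a partial check.** ASA may stand in for some missed disease, and the plan explains why earlier years cannot be covered. But c) uses 4 of 11 years and the same NPR-only score. The directed acyclic graph does not help here: it selects variables and does not improve a poorly measured one.

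**Timing.** A reader might also infer that complications of the index stay will be counted as comorbidity, since no look-back is stated. The plan does not say so, and an analyst building a comorbidity score would normally avoid it. Excluding the whole index stay could even discard chronic conditions coded only there.

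**Conclusion.** The point holds as a worthwhile, inexpensive improvement in how a confounder is measured. The facts are clear from the text: one hospital-based comorbidity source, no BMI or ASA in the primary models, and a prescription register spanning the study period whose only stated use is post-revision antibiotics.

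The consequence is conditional. Residual confounding arises only if under-captured conditions differ between LAF and TAF rooms after the other adjustments. For one condition under the assumed central inputs, the spurious hazard ratio is about 1.015-1.024 and the error rate roughly 5.4-6.8%. It falls to zero with balance and is larger with greater imbalance or poorer capture. The direction is unknown. Nothing here makes the planned analysis invalid.

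**What to change.** In Variables and in the confounder list under Statistical analysis, add a few comorbidity indicators from DNPR prescriptions redeemed in a fixed window before the operation date, for example 12 months. Candidate groups are glucose-lowering drugs, systemic glucocorticoids, immunosuppressants or antirheumatics, and drugs for obstructive lung disease. Enter them beside the NPR Elixhauser score in the Cox models. At minimum, prespecify a sensitivity analysis of the primary endpoint over the full 2010-2020 period that includes them.

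The cost is a wider extract of ATC codes from a register already in the plan, possibly an addition to the data approval, and a few more model terms against an assumed 650 to 1,120 events. No new patients or procedures are needed.

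A useful clarification, though not the basis of this point: state one fixed look-back for NPR diagnoses, and state that acute complications of the index stay do not count as comorbidity.
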